### Ibrutinib (supplied by Pharmacyclics):

#### Interrupt or discontinue therapy

- Interrupt therapy for any non-hematological toxicity  $\geq$ Grade 3, neutropenia with infection or fever  $\geq$ Grade 3, or Grade 4 hematological toxicities
- Reinitiate ibrutinib at the starting dose (indicated specific) once toxicities have resolved to Grade 1 or baseline (recovery)
- If the toxicity reoccurs, reduce dose by 1 capsule (140 mg/day)
- A second reduction of dose by 140 mg may be considered as needed
- Discontinue if these toxicities persist or recur following 2 dose reductions

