**Brentuximab vedotin (commercial supply):**

**Peripheral Neuropathy:** Peripheral neuropathy should be managed using a combination of dose delay and reduction to 1.2 mg/kg. For new or worsening Grade 2 or 3 neuropathy, dosing should be held until neuropathy improves to Grade 1 or baseline and then restarted at 1.2 mg/kg. For Grade 4 peripheral neuropathy, BV should be discontinued.

**Neutropenia:** Neutropenia should be managed by dose delays and reductions. For grade 1 or 2, continue at same dose. The dose of BV should be held for Grade 3 or 4 neutropenia until resolution to baseline or Grade 2 or lower. Growth factor support should be considered for subsequent cycles in patients who experience Grade 3 or 4 neutropenia. In patients with recurrent Grade 4 neutropenia despite the use of growth factors, and despite dose reduction specified for ibrutinib, discontinuation or dose reduction of BV to 1.2 mg/kg may be considered.

**Anemia and thrombocytopenia:** For Grade 1 or 2, continue at same dose. For Grade 3 and 4, withhold dose until toxicity is  $\leq$  Grade 2 or has returned to baseline, then resume treatment at the same dose level. For second occurrence of Grade 4, withhold until toxicity  $\leq$  Grade 1 or has returned to baseline, then resume treatment at 1.8 mg/kg but reduce ibrutinib dose from 560 mg to 420 mg. For third occurrence, withhold until toxicity  $\leq$  grade 1 or has returned to baseline, then resume BV at 1.8 mg/kg but reduce ibrutinib dose from 420 mg to 280 mg. In patients with recurrent grade 4 anemia and thrombocytopenia despite dose reduction specified for ibrutinib, then resume treatment of BV at 1.2 mg/kg. If patient was already at 1.2 mg/kg of BV, then discontinue treatment of BV and ibrutinib.

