**Other non-hematological toxicities:** For Grade 1 or 2, continue at same dose. For Grade 3, withhold dose until toxicity is  $\leq$  Grade 1 or has returned to baseline, then resume treatment at the same dose level. For Grade 4, withhold until toxicity  $\leq$  Grade 1 or has returned to baseline, then resume treatment at same dose level but reduce ibrutinib dose from 560 mg to 420 mg. For second occurrence of Grade 3, withhold dose until toxicity  $\leq$  Grade 1 or has returned to baseline, then resume BV at same dose level, but reduce ibrutinib from 560 mg to 420 mg. For second occurrence of Grade 4, withhold until toxicity  $<$  Grade 1 or has returned to baseline, then resume BV at same dose level but reduce ibrutinib from 420 mg to 280 mg. For third occurrence of Grade 3, withhold dose until toxicity  $<$  Grade 1 or has returned to baseline, then resume BV at same dose level but reduce ibrutinib from 420 mg to 280 mg. For third occurrence of grade 4 toxicity, discontinue ibrutinib. In patients with recurrent grade 3 and 4 non hematological toxicities despite dose reduction specified for ibrutinib, then reduce treatment of BV to 1.2 mg/kg. If patient was already at 1.2 mg/kg of BV, then discontinue treatment of BV and ibrutinib.

The start of the next cycle may be delayed for up to 3 weeks if additional time is required for the patient to recover from study treatment-associated toxicity experienced during the current cycle. Delays of greater than 3 weeks are prohibited without approval of the PI.

Doses reduced for drug-related toxicity should generally not be re-escalated. However, intra-patient re-escalation to the previous dose level may be permitted at the discretion of the PI.

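### Section 6.2 gives two ibrutinib restart doses after a first Grade 4 non-hematologic event (560 mg or 420 mg) and does not say which governs

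*Combined protocol and SAP*

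**What the plan says.** Section 6.2 opens with a priority rule: ibrutinib is reduced before BV, except for peripheral neuropathy, where BV is reduced first. Specific blocks follow.

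**Ibrutinib block** (Interrupt or discontinue therapy). It applies to any non-hematologic toxicity of Grade 3 or higher, so Grade 4 is included. After a first event the site is told: "Reinitiate ibrutinib at the starting dose (indicated specific) once toxicities have resolved to Grade 1 or baseline (recovery". The step down comes only with a repeat event, where the instruction is: "If the toxicity reoccurs, reduce dose by 1 capsule (140 mg/day". A further cut of the same size is optional. The block ends with a stopping rule that carries no condition on the BV dose: "Discontinue if these toxicities persist or recur following 2 dose reductions".

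**Other non-hematological toxicities**, under the BV heading. For a first Grade 4 event the dose is held until recovery, "then resume treatment at same dose level but reduce ibrutinib dose from 560 mg to 420 mg". A second Grade 4 event takes ibrutinib from 420 to 280 mg. Then: "For third occurrence of grade 4 toxicity, discontinue ibrutinib". The paragraph goes on to cover recurrent Grade 3 and 4 toxicity "despite dose reduction specified for ibrutinib, then reduce treatment of BV to 1.2 mg/kg", and stops both drugs if BV is already at 1.2 mg/kg.

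**Anemia and thrombocytopenia**, under the same BV heading. Ibrutinib is cut from 560 to 420 mg at a second Grade 4 event and from 420 to 280 mg at the third. For recurrent Grade 4 toxicity "despite dose reduction specified for ibrutinib, then resume treatment of BV at 1.2 mg/kg", both drugs again stop if BV is already at 1.2 mg/kg.

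**The concern.** The same Grade 4 non-hematologic event falls under both the ibrutinib block and the paragraph on other non-hematological toxicities, and the two give different doses. The layout makes the less cautious answer easy to reach: someone looking up how to restart ibrutinib will go to the block headed ibrutinib, which returns the patient to full dose, while the stricter ibrutinib instruction sits under BV.

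The protocol synopsis lists four participating sites. Each could follow the text and give patients with the same life-threatening event different doses. Section 14.1.1 defines a deviation as divergence from a specific protocol element, so whichever dose is chosen departs from one of the two instructions. Safety and tolerability, including the time course and duration of toxicities, are a secondary objective (Section 1.0), and uneven rechallenge doses make those data harder to interpret.

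**Working it through.** No sample size, error rate or event count enters this point. The check traces the two ladders and compares them.

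**Inputs.** Starting dose 560 mg daily, the expected phase II dose (synopsis, dosage and administration). Capsule step 140 mg and cycle length 21 days (Sections 5.1.5 and 5.1.7). The patient has Grade 4 non-hematologic toxicity other than neuropathy, and the same toxicity recurs each time.

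| Event | Ibrutinib block | Other non-hematological toxicities | Difference |
|---|---|---|---|
| First | 560 mg | 560 − 140 = 420 mg | 140 mg/day; 140/420 = 33%; 140 × 21 = 2,940 mg per cycle |
| Second | 560 − 140 = 420 mg | 420 − 140 = 280 mg | 140 mg/day; 140/280 = 50%; 2,940 mg per cycle |
| Third | 420 − 140 = 280 mg if the optional cut is made, otherwise 420 mg | stop | 280 × 21 = 5,880 or 420 × 21 = 8,820 mg per cycle |

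All three rows have one cause: the second ladder is the first one started a step earlier.

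**Where the blocks agree.** For Grade 3 non-hematologic toxicity, and for Grade 4 anemia or thrombocytopenia, both routes give 560, 420 and 280 mg after the first, second and third events, if the optional second cut is taken. The direct conflict is therefore confined to Grade 4 non-hematologic events.

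**Does other text resolve it?** The opening priority rule chooses between ibrutinib and BV, not between ibrutinib doses. The paragraph on both drugs together deals with timing. The closing text on re-escalation presupposes a reduction; the question here is whether one was required.

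**Tension inside the stricter paragraph.** A third Grade 4 event stops ibrutinib. The next sentence again names Grades 3 and 4, moves to a BV cut, and mentions stopping ibrutinib only when BV is already at 1.2 mg/kg. Read alone, it could appear to undo the stop.

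**Patients who start at 420 mg.** The reduction steps under the BV heading are written only as 560 to 420 and 420 to 280 mg, so they give no first cut from a 420 mg start. The synopsis plans at least three such patients in the lead-in. If 560 mg is not declared safe and 420 mg is carried forward under Section 11.1.2, the gap would reach the phase II patients. The ibrutinib block's one-capsule wording does work for them: 420, then 420 − 140 = 280, then 280 − 140 = 140 mg.

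**The case against.** The strongest reply is that a specific rule displaces a general one. The ibrutinib block is general, whereas the other paragraph goes grade by grade and occurrence by occurrence and names this trial's doses. That is a reasonable reading and would settle the matter in favor of 420 mg. But the protocol does not state it, and the placement of the stricter rule under the BV heading works against it. The Protocol Management Team, recommended to meet at least monthly (Section 15.3), offers a forum for such questions, but it does not replace a clear instruction at the time of restart.

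Several stronger readings are tempting and should not be made:

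- *Three separate contradictions.* The second and third differences follow mechanically from the first.
- *A direct contradiction once ibrutinib has been cut twice.* The ibrutinib block then discontinues ibrutinib, while the paragraphs under the BV heading cut BV to 1.2 mg/kg. Those paragraphs never say that ibrutinib continues; that is inferred from their stopping both drugs when BV is already at 1.2 mg/kg. A site could satisfy both texts by stopping ibrutinib and giving BV at 1.2 mg/kg. This is an ambiguity.
- *No reduction rule for 420 mg starters.* The ibrutinib block supplies one; only the fixed-dose steps under the BV heading fail.
- *A quantified chance that the conflict will arise.* The documents give no Grade 4 non-hematologic rate for the combination, so any such figure would rest on an assumed rate.

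**Conclusion.** The conflict is real and limited. For a patient who starts at 560 mg and has Grade 4 non-hematologic toxicity other than peripheral neuropathy, Section 6.2 supports both 560 and 420 mg after the first event, and the one-step offset persists until ibrutinib is stopped. The excess under the ibrutinib block is 140 mg/day after a first or second event. After a third it is 280 or 420 mg/day against none. How many patients would be affected cannot be stated from the documents.

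This should be corrected because a site following the text may resume full dose after a life-threatening event. The missing first cut for 420 mg starters is secondary, and the position after two ibrutinib cuts needs only clarification.

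A reader might infer that the efficacy result is at risk. The documents do not support that: the complete response analysis, the 39-patient sample size and the two-stage cutoffs do not depend on the restart dose, and an event in cycle 1 that meets the unacceptable-toxicity definition counts toward the rule in Section 11.3 whichever dose follows.

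**What to change.** 1. In the ibrutinib block of Section 6.2, add: *Exception: for Grade 4 non-hematologic toxicity other than peripheral neuropathy, follow Other non-hematological toxicities: reduce ibrutinib by one capsule (140 mg) after the first event and by another after the second, and discontinue ibrutinib at the third.* This adopts the stricter ladder already in the protocol.
2. In the paragraph on other non-hematological toxicities, limit the sentence on recurrence despite ibrutinib reduction, for example by adding: *This does not override discontinuation of ibrutinib at a third Grade 4 event.*
3. Secondary: in that paragraph and the one on anemia and thrombocytopenia, replace the fixed steps (560 to 420, 420 to 280 mg) with one-capsule reductions, as in the ibrutinib block. For a 420 mg starter this reaches 140 mg, below the 280 mg now named under the BV heading, so the sponsor should confirm that 140 mg is an acceptable floor.
4. Clarification: state whether ibrutinib stops or continues when other toxicity recurs after two ibrutinib cuts and BV is lowered to 1.2 mg/kg. That choice is the sponsor's.

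The cost is a few sentences of protocol text. The clinical downside is that some patients receive 140 mg/day less ibrutinib after a first or second Grade 4 event than the ibrutinib block now allows, and none after a third.

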## **7.0 Agent Information and Risks**

---

### **7.1 7.1 Brentuximab vedotin**

#### **7.1.1 Description**

Brentuximab vedotin (BV), is also named SGN-35, or Adcetris. BV is an antibody-drug conjugate consisting of the anti-CD30 antibody cAC10 conjugated to MMAE, an anti-tubulin agent. BV is a sterile, preservative-free, white to off-white lyophilized cake for reconstitution for IV administration. It is supplied by Seattle Genetics in single-use, Type 1 borosilicate glass vials with FluroTec®-coated butyl rubber stoppers and aluminum seals. Each vial of the product contains BV, trehalose, sodium citrate, and polysorbate 80.

#### **7.1.2 Toxicology**

The toxicity of multiple doses of brentuximab vedotin has been assessed in rats and monkeys. In both species, hypocellularity of the bone marrow and lymphoid depletion of the thymus were observed. Histopathologic lesions were also observed in the spleen in monkeys and in the liver and testes in rats. In addition, decreases in peripheral blood counts were observed in both species, and elevations in liver enzymes were seen in rats only. The most significant clinical toxicity was neutropenia, observed in monkeys, which resulted in secondary bacterial infections leading to early deaths at the 6 mg/kg dose. Toxicity was dose-dependent, with a no-observable-adverse-effect level of 0.5 mg/kg in rats and 1 mg/kg in monkeys. See the brentuximab vedotin SGN-35 Investigator's Brochure for details of the toxicology data.

[figure not shown]
#### **7.1.3 Pharmacology – Handling, Storage, Dispensing and Disposal**

BV will be from a commercial supply. Please see package insert for dose preparation and storage information.

### **7.2 Ibrutinib**

#### **7.2.1 Description**

Ibutinib is also named Imbruvica. It is an inhibitor of Bruton's tyrosine kinase. It is a small molecule with the molecular formula C25H24N6O2 and a molecular weight of 440.5. Ibrutinib capsules for oral administration are supplied as gray opaque capsules that contain 140 mg ibrutinib as the active ingredient. The inactive ingredients are croscarmellose sodium, magnesium stearate, microcrystalline cellulose, and sodium lauryl sulfate.

**Figure 1. Ibrutinib**

## 7.2.2 Toxicology

In safety pharmacology assessments, no treatment-related effects were observed in the central nervous system or respiratory system in rats at any dose tested. Further, no treatment-related corrected QT interval (QTc) prolongation effect was observed at any tested dose in a cardiovascular study using telemetry-monitored dogs.

On the basis of data from rats and dogs, including general toxicity studies up to 13 weeks duration, the greatest potential for human toxicity with ibrutinib is predicted to be in lymphoid tissues (lymphoid depletion) and the gastrointestinal tract (soft feces/diarrhea with or without inflammation). Additional toxicity findings seen in only one species with no observed human correlate in clinical studies to date include pancreatic acinar cell atrophy (rat), minimally decreased trabecular and cortical bone (rat), and corneal dystrophy (dog).

In vitro and in vivo genetic toxicity studies showed that ibrutinib is not genotoxic. In a rat embryo-fetal toxicity study, ibrutinib administration was associated with fetal loss and malformations (teratogenicity) at ibrutinib doses that result in approximately 6 times and 14 times the exposure (AUC) in patients administered the daily doses of 420 and 560 mg, respectively.

## 7.2.3 Pharmacology-Handling, Storage, Dispensing, and Disposal:

Ibrutinib capsules are provided as a hard gelatin capsule containing 140 mg of ibrutinib. All formulation excipients are compendial and are commonly used in oral formulations. Refer to the ibrutinib Investigator's Brochure for a list of excipients.

The ibrutinib capsules will be packaged in opaque high-density polyethylene plastic bottles with labels bearing the appropriate label text as required by governing regulatory agencies. All of the study drug will be dispensed in child-resistant packaging.

Refer to product label for additional guidance on study drug storage, preparation dispensing, handling and disposal.

## **8.0 Correlative/Special Studies**

---

Each subject will have either a fresh core or excisional biopsy of a tumor lesion prior to starting study therapy or will have available archival tissue from a biopsy that was performed after the most recent therapy and within 3 months of the screening date. If feasible, all subjects will also undergo biopsy of a tumor lesion at the time of disease progression.

Guidelines for tumor sampling are as follows:

- For fresh biopsies:
  - a. For core biopsies, 2 core biopsy tumor samples will be immediately frozen and processed
  - b. For excisional biopsies, an approximately 5mm x 5mm tumor sample will be immediately frozen and processed
  - c. The remainder of the specimen will be processed in a routine fashion by hematopathology. Using the formalin-fixed paraffin embedded (FFPE) tissue block, the following samples will be processed for correlative studies:
    - i. 10 x 5 micron paraffin slices
    - ii. 10 x 5 micron unstained slides
- Fresh or frozen tissue from excisional biopsies or 2-3 needle cores will be minced into smaller fragments. Using a lysis buffer, the nuclei will be released and isolated using a gradient solution. The pelleted nuclei will then be stained with DAPI and sorted by flow cytometry by DNA content/ploidy at the City of Hope Cytometry Core. The supernatant from the gradient, which

contains the cytoplasmic contents of the Hodgkin cells and inflammatory background cells, will be saved for RNA extraction. DNA will be extracted from the Hodgkin nuclei as well as normal/diploid, and the paired samples will be evaluated by whole exome sequencing.

- FFPE tissue blocks will be examined for CD30 expression, drug exporter expression, and CD68 tumor macrophages. We will also isolate DNA/RNA from inflammatory cells in the microenvironment and perform gene expression profiling signatures.
- We will also obtain tumor biopsies from patients who develop progressive disease while on treatment. We will test for CD30 and drug exporter expression by immunohistochemistry and will compare with the pre-treatment sample. We will also perform gene expression profiling on post-treatment relapse samples and compare with pre-treatment samples.
- For archival specimens:
  - a. Using the formalin-fixed paraffin embedded (FFPE) tissue block, the following samples will be processed for correlative studies:
    - i. 10 x 5 micron paraffin slices
    - ii. 10 x 5 micron unstained slides

For non COH sites refer to [Appendix 3](#) for tissue shipping guidelines.

- For peripheral blood collections:
  - a. 36 ml of peripheral blood will be drawn on day 1 prior to dosing, day 8 during cycle 1, and on day 1 cycle 2 prior to dosing. They will be analyzed for:
    - i. T/B/NK cell subsets. 20 ml of blood will be drawn in sodium heparin tube. They will be sent to [name] lab at COH. 8-color flow cytometric analysis will be performed to phenotype immune cell subsets and functional readouts. A prototype BD microfluidic FACS instrument that can analyze small cell numbers will be used. Markers to be assessed: TIGIT, PD-1, CD45, CD4, CD8, CD103, CD69, and CCR7. BTK and ITK occupancy will also be evaluated Leftover blood to be processed into viable cryopreserved PBMCs and stored for future analysis. For non COH sites, refer to Appendix 5 for blood shipping guidelines.
    - ii. ITK and BTK occupancy will be assessed by Pharmacyclics. See [Appendix 2](#) for instructions. 2 x 8 ml CPT citrate tube whole blood (PBMC and plasma) to support BTK/ITK occupancy and optional retrospective cytokine/chemokine testing at PCYC.

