Data from Study PCYC-04753 demonstrate that, although ibrutinib is rapidly eliminated from the plasma after oral administration, once daily dosing with ibrutinib is adequate to sustain maximal pharmacodynamic activity for 24 hours post dose at dose levels  $\geq 2.5$  mg/kg. In this study, the BTK occupancies for the 2.5 mg/kg/day to 12.5 mg/kg/day cohorts and for the 560 mg continuous dosing cohort were all above 90% at either 4 or 24 hours after drug administration.

For the most comprehensive nonclinical and clinical information regarding ibrutinib background, safety, efficacy, and in vitro and in vivo preclinical activity and toxicology, refer to the latest version of the ibrutinib Investigator's Brochure.

We performed a synergy assay testing the combination of ibrutinib and brentuximab vedotin (SGN-35) in L428 (HL cell line) and found a synergistic effect. The CI was 0.253 for brentuximab vedotin 1: ibrutinib 1, which is highly synergistic. Ibrutinib is also an ITK inhibitor, which can be active against activated T cells. It is possible that ibrutinib can inhibit B cells and T cells in the microenvironment of HL. Because of our in vitro synergy data, and because the two agents have a tolerable toxicity profile with little overlap, we propose a phase II study of ibrutinib plus brentuximab vedotin in patients with relapsed/refractory HL.

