### 11.5 Analysis of Correlative Endpoints:

Because of the limited sample size inherent to phase II studies, the analysis of correlative endpoints is primarily exploratory. Standard descriptive methods will be used to summarize: 1) the role of CD30, CD68, and drug exporters on lymphoma specimens and 2) the role of T/B/NK cell subsets and BTK and ITK occupancy in the peripheral blood. If the combination is not found to have sufficient activity, these patterns may help explain the lack of activity. If sufficient activity is found, then participants who experience an objective response will be compared to those who did not in terms of correlates. Estimates of variation will also prove useful for future clinical research on this regimen. Formal testing of these comparisons is not planned. All analysis will clearly document the exploratory nature of these studies, although no attempt will be made to adjust for multiple comparisons inherent in correlative studies.

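### The eight flow markers listed in Section 8.0 do not separately identify B or NK cells, so the T/B/NK subset summary planned in Section 11.5 cannot be produced for those two lineages from the assay as specified.

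*Combined protocol and SAP*

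**What the plan says.** Section 8.0 (Correlative/Special Studies) sets the blood collection: "36 ml of peripheral blood will be drawn on day 1 prior to dosing, day 8 during cycle 1, and on day 1 cycle 2" (the last also before dosing). The first use of that blood is given as "T/B/NK cell subsets. 20 ml of blood will be drawn in sodium heparin tube". The method follows: "8-color flow cytometric analysis will be performed to phenotype immune cell subsets and functional readouts". The marker list is then stated: "Markers to be assessed: TIGIT, PD-1, CD45, CD4, CD8, CD103, CD69, and CCR7". What remains is banked: "Leftover blood to be processed into viable cryopreserved PBMCs and stored for future analysis". The second use of the draw is separate: "2 x 8 ml CPT citrate tube whole blood (PBMC and plasma) to support BTK/ITK occupancy", with optional cytokine and chemokine testing.

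Section 11.5 (Analysis of Correlative Endpoints) commits to a descriptive summary of "the role of T/B/NK cell subsets and BTK and ITK occupancy in the peripheral blood". If the combination lacks activity, these patterns are meant to help explain why. If it is active enough, objective responders are to be compared with the other participants on the correlates. No formal tests are planned.

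The rationale in Section 2.1 (Ibrutinib) names two lineages: "It is possible that ibrutinib can inhibit B cells and T cells in the microenvironment of HL".

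**The concern.** The stated analysis asks for three lineages, while the stated assay lists markers suited to one. Anyone who ran Section 8.0 as written and then turned to Section 11.5 would have no B-cell or NK-cell variable to summarise or compare.

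The gap is awkward for this drug. Section 2.1 describes ibrutinib as a BTK inhibitor and places the main functional role of BTK in B-cell antigen receptor signalling, so the B cell is the lineage most directly tied to the target. If the trial were negative, the B and NK patterns that Section 11.5 hopes might help explain the result would be missing. The first draw is taken before dosing and cannot be repeated once treatment has begun.

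**Working it through.** The check is a count and a side-by-side reading. No sample-size or error-rate formula applies.

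**1. The plan's own volume figure.** Section 8.0 gives 36 ml per draw. Its components are 20 ml heparin + 2 × 8 ml CPT citrate = 20 + 16 = 36 ml. This reproduces, and it shows that the 20 ml heparin tube is the allocation for subsets.

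**2. Markers against colours.** The list is TIGIT, PD-1, CD45, CD4, CD8, CD103, CD69 and CCR7: 8 markers. The method has 8 colours, and 8 − 8 = 0. If all eight are run in one tube, no colour is free. The number of tubes is not stated, but splitting the same eight markers over several tubes adds no new marker.

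**3. What each marker can identify.** This step uses general flow-cytometry knowledge, which the documents do not state.

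| Marker | Identifies | Defines B? | Defines NK? |
|---|---|---|---|
| CD45 | leukocytes in general | no | no |
| CD4, CD8 | T-cell subsets | no | no |
| TIGIT, PD-1, CD69 | checkpoint or activation state | no | no |
| CD103, CCR7 | residency or homing | no | no |

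Overlap with the usual B-cell markers (CD19, CD20, CD22, CD79a) is 0. Overlap with the usual NK markers (CD56, CD16, CD57, NKp46) is 0. Cells negative for both CD4 and CD8 would be a mixture of B, NK and other cells. Because CD3 is absent, CD8-positive NK cells would be counted with CD8 T cells, by an amount the list cannot measure and the documents do not give.

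**4. Assay against analysis.**

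| Lineage in Section 11.5 | Available from the Section 8.0 list? |
|---|---|
| T | partly: CD4 and CD8 subsets, without CD3 |
| B | no |
| NK | no |

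**5. Extent.** If all three draws are made, 39 phase II patients give 39 × 3 = 117 heparin samples. Stopping after stage 1 gives 19 × 3 = 57. If the 9 expected lead-in patients are additional and are sampled, the figure is (39 + 9) × 3 = 144.

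**6. Room for a remedy.** Adding one B and one NK marker to the present list needs 8 + 2 = 10 colours, or 11 with CD3, both above 8. A separate tube with CD45, CD3, one B marker and one NK marker needs 4, which fits.

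**The case against.** The strongest reply is that Section 8.0 is not a full staining specification. It promises functional readouts without naming reagents for them, gives no number of tubes and does not call the list exhaustive. The table of contents also lists appendices on pharmacodynamic sample collection and blood shipping that are not in the text available here. This stands as a reason for caution about what the laboratory intends. It does not remove the conflict on the page: the list is introduced as the markers to be assessed, and the available text names no second panel and no B or NK marker.

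Four stronger readings might be inferred, and the documents do not support them.

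- *The samples themselves cannot yield B or NK data.* Viable leftover cells are banked and could be stained later. That depends on there being leftover material, and the storage is for unspecified future work.
- *No channel is left for a lineage marker.* This assumes a single tube.
- *Blood is drawn for nothing.* The same draw supports CD4/CD8 phenotyping, BTK and ITK occupancy, and banking. Occupancy also addresses binding of the drug to its target directly, though it is not a B-cell count or phenotype.
- *The trial's mechanistic rationale goes untested.* Section 2.1 speaks of cells in the tumour microenvironment, and the tissue studies in Section 8.0 examine that compartment.

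It is also fair that the exploratory objective in Section 1.0 is to collect DNA/RNA and plasma, and does not name these subsets. The commitment comes from Sections 8.0 and 11.5.

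**Conclusion.** The point holds as a conflict between a stated assay and a stated analysis. With the eight listed markers, B and NK cells (2 of the 3 named lineages) cannot be separately identified at any of the three draws, and the planned summary and responder comparison cannot be produced for them. The T-cell part is usable, with the limitation that CD3 is missing.

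The impact is low. Section 11.5 is exploratory and descriptive; the complete response endpoint, the two-stage design, the safety rules and patient safety are untouched. The sample counts above show reach only. None is a firm maximum, because lead-in patients may be additional and not every draw need be made.

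The conclusion assumes that the list in Section 8.0 is what will be run, that the usual lineage markers are as described above, and that no appendix outside the available text adds a panel.

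**What to change.** Reconcile Section 8.0 with Section 11.5 in one of two ways.

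1. **Keep the three lineages.** In Section 8.0, add a lineage stain on the same 20 ml heparin sample, for example CD45, CD3, a B-cell marker such as CD19 and an NK-cell marker such as CD56, and keep the present list for T-cell phenotype. State the number of tubes. The cost is reagents for one more stain per sample and some cells that would otherwise be banked. If the 20 ml suffices, no extra draw, visit or patient is needed. For samples already taken, state whether banked cells will be stained and what happens where none remain.
2. **Narrow the claim.** In Sections 8.0 and 11.5, replace the T/B/NK wording with CD4 and CD8 T-cell subsets, and note that without CD3 the CD8 population may include NK cells. This costs a wording change only.

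If a broader panel is already intended, one sentence in Section 8.0 naming its B and NK markers settles the matter.
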